#### **11.5.2.3 Phase Ib**

Tumor biopsies are mandatory for patients in Phase Ib with safely accessible soft tissue and/or visceral metastases. Biopsies should be obtained predose and after 2 weeks of treatment (Cycle 1 Day  $15 \pm 1$  day, during the period between  $\geq 2$  and  $\leq 12$  hours postdose) *and at the time of disease progression*.

#### **11.5.2.4      Archival Tissue Collection**

Archival paraffin-embedded tissue may be collected to evaluate the histology of the tumor in all Phases of this study (Ia, Ib, IIa) for DNA and /or RNA extraction to enable next generation sequencing (NGS) for exploratory research on non-inherited biomarkers (including, but not limited to, cancer-related genes and biomarkers associated with common molecular pathways). If fresh tumor tissue biopsy cannot be obtained at screening, every reasonable effort should be made to obtain the most recent archival tissue sample. Tumor blocks are preferred, but in the event that local regulations prevent the shipment of tumor blocks, 15–20 unstained, serially cut slides are requested. Minimum tissue requirements are further described in the laboratory manual. Cytological, fine-needle aspiration, and decalcified bone biopsy samples are not acceptable. Tissue blocks from archival biopsies will be returned to the archival facility from which they were originally received.

#### **11.5.3      Circulating Tumor DNA Analyses**

In Phase Ia and IIa, additional blood samples will be collected at screening and at the time of study discontinuation for analysis of circulating tumor DNA (ctDNA). During Phase IIa, ctDNA will also be collected at Cycle 3.

In Phase Ib, additional blood samples will be collected at screening, Cycle 3, Cycle 5, and at the time of study discontinuation for analysis of ctDNA.

Recent nonclinical and clinical data suggest that mutations in ER- $\alpha$  and phosphatidylinositol-4,5-bisphosphate 3-kinase, catalytic subunit alpha (PIK3CA) are associated with endocrine resistant breast cancer. To gain insights into potential causal relationships between GDC-0810's clinical activity and resistance mechanisms, mutational status of both of these genes will be monitored in ctDNA isolated from plasma using next generation sequencing *and other molecular technologies*.

#### **11.5.4      Pharmacogenomic (PGx) Evaluations**

It is established that genetic variants of drug-metabolizing enzymes and transporters can affect the PK of drugs, affecting their safety and efficacy. For example, patients who carry defective alleles of the gene encoding uridine diphosphate glucuronosyltransferase 1A1, which facilitates the metabolism and excretion of SN-38 (the active metabolite of irinotecan), are at higher risk for adverse effects associated with the use of standard doses of irinotecan ([O'Dwyer et al. 2006](#)). Similarly, it has recently been shown that patients with genetic polymorphisms in the gene that encodes cytidine deaminase have decreased clearance of gemcitabine and an increased incidence of neutropenia when they received platinum containing drugs or fluorouracil concurrently ([Sugiyama et al. 2007](#)).

For potential PGx analysis of genes that may affect the PK and safety of GDC-0810, a mandatory blood sample for DNA isolation will be collected from all patients in Phase IIa and Ib portions of this study prior to the first dose of GDC-0810 on Cycle 1 Day 1.

## **12. SAFETY ASSESSMENTS**

### **12.1 SAFETY PARAMETERS AND DEFINITIONS**

Safety assessments will consist of monitoring and recording adverse events, including serious adverse events and non-serious adverse events of special interest, performing protocol-specified safety laboratory assessments, measuring protocol-specified vital signs, and conducting other protocol-specified tests that are deemed critical to the safety evaluation of the study.

Certain types of events require immediate reporting to the Sponsor, as outlined in Section [12.3](#).

#### **12.1.1 Adverse Events**

According to the International Conference on Harmonisation (ICH) guideline for Good Clinical Practice (GCP), an adverse event is any untoward medical occurrence in a clinical investigation subject administered a pharmaceutical product, regardless of causal attribution. An adverse event can therefore be any of the following:

- Any unfavorable and unintended sign (including an abnormal laboratory finding), symptom, or disease temporally associated with the use of a medicinal product, whether or not considered related to the medicinal product
- Any new disease or exacerbation of an existing disease (a worsening in the character, frequency, or severity of a known condition), except as described Section [12.3](#)
- Recurrence of an intermittent medical condition (e.g., headache) not present at baseline
- Any deterioration in a laboratory value or other clinical test (e.g., ECG, X-ray) that is associated with symptoms or leads to a change in study treatment or concomitant treatment or discontinuation from study drug
- Adverse events that are related to a protocol-mandated intervention, including those that occur prior to assignment of study treatment (e.g., screening invasive procedures such as biopsies)

#### **12.1.2 Serious Adverse Events (Immediately Reportable to the Sponsor)**

A serious adverse event is any adverse event that meets any of the following criteria:

- Fatal (i.e., the adverse event actually causes or leads to death)
- Life threatening (i.e., the adverse event, in the view of the investigator, places the patient at immediate risk of death)

This does not include any adverse event that had it occurred in a more severe form or was allowed to continue might have caused death.

- Requires or prolongs inpatient hospitalization (see Section [12.2.5.10](#))

- Results in persistent or significant disability/incapacity (i.e., the adverse event results in substantial disruption of the patient's ability to conduct normal life functions)
- Congenital anomaly/birth defect in a neonate/infant born to a mother exposed to study drug
- Significant medical event in the investigator's judgment (e.g., may jeopardize the patient or may require medical/surgical intervention to prevent one of the outcomes listed above)

The terms "severe" and "serious" are not synonymous. Severity refers to the intensity of an adverse event (e.g., rated as mild, moderate, or severe, or according to NCI CTCAE; see Section 12.2.3); the event itself may be of relatively minor medical significance (such as severe headache without any further findings).

Severity and seriousness need to be independently assessed for each adverse event recorded on the eCRF.

Serious adverse events are required to be reported by the investigator to the Sponsor immediately (i.e., no more than 24 hours after learning of the event; see Section 12.3 for reporting instructions).

### **12.1.3      Non-Serious Adverse Events of Special Interest (Immediately Reportable to the Sponsor)**

Non-serious adverse events of special interest are required to be reported by the investigator to the Sponsor immediately, irrespective of severity or regulatory seriousness (i.e., no more than 24 hours after learning of the event; see Section 12.3 for reporting instructions). Adverse events of special interest for this study include the following:

#### **General Drug Development Adverse Events**

- Cases of potential drug-induced liver injury that include an elevated ALT or AST in combination with either an elevated bilirubin or clinical jaundice, as defined by Hy's Law (see Section 12.3)
- Suspected transmission of an infectious agent by the study drug, as defined below:
 

Any organism, virus, or infectious particle (e.g., prion protein transmitting transmissible spongiform encephalopathy), pathogenic or non-pathogenic, is considered an infectious agent. A transmission of an infectious agent may be suspected from clinical symptoms or laboratory findings that indicate an infection in a patient exposed to a medicinal product. This term applies only when a contamination of the study drug is suspected.

#### **Adverse Events of Interest**

- DLTs occurring during the DLT assessment window
- Grade  $\geq 2$  vomiting/diarrhea

- Grade  $\geq$  3 nausea
- Grade  $\geq$  2 thromboembolic events (including pulmonary embolism)
- Grade  $\geq$  2 vaginal or uterine hemorrhage
- Grade  $\geq$  3 elevation of ALT or AST

**Adverse Events of Special Interest for Patients *Assigned* to Receive GDC-0810 in Combination with Palbociclib**

- Grade 4 neutropenia, thrombocytopenia, or anemia
- Any grade febrile neutropenia

**12.2 METHODS AND TIMING FOR CAPTURING AND ASSESSING SAFETY PARAMETERS**

The investigator is responsible for ensuring that all adverse events (see Section 12.1.1 for definition) are recorded on the Adverse Event eCRF and reported to the Sponsor in accordance with instructions provided in this section and in Section 12.3.2).

For each adverse event recorded on the Adverse Event eCRF, the investigator will make an assessment of seriousness (see Section 12.1.2 for seriousness criteria), severity (see Section 12.2.3), and causality (see Section 12.2.4).

**12.2.1 Adverse Event Reporting Period**

Investigators will seek information on adverse events at each patient contact. All adverse events, whether reported by the patient or noted by study personnel, will be recorded in the patient's medical record and on the Adverse Event eCRF.

**After informed consent** has been obtained **but prior to initiation of study drug**, only serious adverse events caused by a protocol-mandated intervention (e.g., invasive procedures such as biopsies, discontinuation of medications) should be reported (see Section 12.3.2 for instructions for reporting serious adverse events).

**After initiation of study drug**, all adverse events will be reported until 28 days after the last dose of study drug. After this period, the investigator should report any serious adverse events that are believed to be related to prior study drug treatment (see Section 12.3.2).

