## 1.2 CLINICAL PK SUMMARY

The clinical pharmacokinetics of GDC-0810 is under investigation in the ongoing clinical Phase Ia/Ila Study GO29642. Preliminary PK information from this study is summarized below.

- GDC-0810 was rapidly absorbed with peak concentrations achieved at 1–3 hours after dosing.
- The mean terminal half-life was approximately 8 hours, and mean apparent oral clearance was 8 L/hour after a single dose of GDC-0810 at 600 mg under the non-fasted condition. Consistent with the half-life, minimal drug accumulation was observed following multiple dosing.
- GDC-0810 exposure in the fasted state increased with dose across the entire dose range tested (100–800 mg).
- In the Phase Ia *portion of the study*, at 600 mg QD, mean $\pm$ SD steady state  $AUC_{0-6}$  and  $C_{max}$  for GDC-0810 was  $41.1 \pm 27.5 \mu\text{g} \cdot \text{hour/mL}$  and  $11.8 \pm 6.61 \mu\text{g/mL}$ , respectively, under the fasted state (n=6), and  $74.9 \pm 30.1 \mu\text{g} \cdot \text{hour/mL}$  and  $25 \pm 8.35 \mu\text{g/mL}$ , respectively, under the nonfasted state (n=5).
- In the Phase Ila *portion of the study*, at the RP2D of 600 mg QD under the fed state, mean $\pm$ SD steady state  $AUC_{0-6}$  and  $C_{max}$  for GDC-0810 was  $39.5 \pm 22.5 \mu\text{g} \cdot \text{hour/mL}$  (n=40) and  $14.3 \pm 7.3 \mu\text{g/mL}$  (n=42), respectively.

Based on pharmacodynamic (PD), clinical tolerability, and preliminary PK data collected to date, once-daily administration of 600 mg under fed conditions (within 30 minutes after eating a meal) was selected as the single-agent RP2D for GDC-0810. See the GDC-0810 Investigator Brochure for further details.

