### **10.4.3 Concomitant Medications and Treatments**

Concomitant therapy includes any medications (*prescription drugs or over-the-counter drugs, herbal or homeopathic remedies, nutritional supplements*) used by a patient from 7 days before screening through the study completion visit.

All concomitant medications administered to the patient will be reported from 7 days before screening through 4 weeks following receipt of the last dose of study drug. The drug name, its route of administration, as well as its start and stop dates will be recorded.

*Any new anti-cancer therapies initiated within the safety follow-up visit (including drug name and date of initiation) will be recorded as well.*

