## **Prohibited Therapies**

No other hormonal therapy, chemotherapy, immunotherapy, or experimental anti-cancer medications will be permitted while the patient is in the study.

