#### **12.3.2.2 Events That Occur after Study Drug Initiation**

After initiation of study drug, serious adverse events and non-serious adverse events of special interest will be reported until 28 days after the last dose of study drug.

*For the Phase Ia portion of the study, the Serious Adverse Event/Adverse Event of Special Interest Reporting Form provided to investigators should be completed and submitted to the Sponsor or its designee immediately (i.e., no more than 24 hours after learning of the event), either by faxing or by scanning and emailing the form using the fax number or email address provided below.*

*For the Phase Ib/IIa portion of the study, investigators should record all case details that can be gathered immediately (i.e., within 24 hours after learning of the event) on the Adverse Event eCRF and submit the report via the electronic data capture (EDC) system. A report will be generated and sent to Safety Risk Management by the EDC system.*

In the event that the EDC system is unavailable, the Serious Adverse Event/Adverse Event of Special Interest Reporting Form provided to investigators should be completed and submitted to the Sponsor or its designee immediately (i.e., no more than 24 hours after learning of the event), either by faxing or by scanning and emailing the form using the contact information below:

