### **15.3.1 Adverse Events**

Adverse events will be graded according to the NCI CTCAE v4.0 and coded to preferred term and system organ class (SOC).

All adverse events reported during the adverse event reporting period will be considered as treatment-emergent adverse events. Incidence rates will be summarized with frequency and percentage by MedDRA SOC and preferred term, with all patients treated as the denominator, unless otherwise specified. In addition, adverse event incidence rates will also be summarized by severity and relationship to study drug.

Treatment-related adverse events are those judged by the Investigator to be at least possibly related to the study drug. Patients with multiple occurrences of events will only be counted once at the maximum severity attributed to study drug for each preferred term, SOC, and overall.

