### **15.3.2 Clinical Laboratory Results**

Normal ranges will be used to identify values that are outside the normal ranges and abnormal laboratory results will be graded according to the NCI CTCAE v4.0.

A shift summary of baseline grade by maximum post-baseline CTCAE grade will be presented, as appropriate. For each laboratory parameter, the baseline laboratory value will be defined as the last laboratory value collected on or prior to the date of the first dose of study drug.

Patients who develop toxicities of Grade  $\geq 3$  will be summarized. Laboratory test results not having CTCAE grade will also be summarized. Parameters that have criteria available for both low and high values (e.g., hypercalcaemia vs. hypocalcaemia) will be summarized for both criteria. Patients will only be counted once for each criterion.

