### Footnotes

- 1. Cycle 2+:** To be performed per institutional guidelines and/or as clinically indicated except for ECOG, physical examination, vital signs, creatinine, liver function tests, adverse events, concomitant medication, and study drug compliance should be monitored at each cycle.
- 2. End of Treatment:** These assessments do not need to be completed if they have been performed within 1 week of study withdrawal (within 4 weeks for imaging studies and 3 months for the transvaginal ultrasound).
- 3. Safety Follow-Up:** Patients should be evaluated for safety up to 28 days after the last dose of study treatment. Physical examination (including ECOG and vitals), hematology, and blood chemistry should be performed as clinically indicated. Adverse events should be followed up until all serious or study drug-related toxicities have resolved or are determined to be "chronic" or "stable", whichever is later.
- 4. Medical History:** Relevant medical history includes clinically significant diseases; smoking history, use of alcohol and drugs of abuse, including history of current disease, surgeries, other pertinent clinical conditions, and information regarding underlying diseases will be recorded at screening.
- 5. Physical Examination:** Examination of major body systems, including known and suspected sites of disease. Height should be collected at Screening.
- 6. CT/MRI of the brain:** To be performed as needed to rule out the presence of untreated CNS metastases.
- 7. Samples for hematology, blood chemistry (except creatinine and liver function tests), and urinalysis** will be performed per institutional guidelines and as clinically indicated. Circulating tumor DNA will be analyzed by a specialty laboratory. The pharmacogenomic analysis of genes that may affect the PK of GDC-0810 and circulating tumor DNA will be analyzed at specialty laboratories. Creatinine and liver function tests should be monitored at each cycle. ctDNA will be collected at screening, Cycle 3, and end of study visit.
- 8. Trough PK Sample:** Plasma samples should be obtained predose on the specified days (patient should not take the study drug at home). Additionally, if clinically feasible, samples should be obtained at the time of any serious and/or unusual adverse events that may be causally related to study drug.

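### Adverse events that start after a new anti-cancer therapy, within 28 days of the last GDC-0810 dose, are counted as treatment-emergent with no cut-off or flag

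*Combined protocol and SAP*

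**What the plan says.** - **Collection.** After study drug starts, "all adverse events will be reported until 28 days after the last dose of study drug" (Section 12.2.1). Section 12.3.2.2 sets the same limit for the expedited categories: "serious adverse events and non-serious adverse events of special interest will be reported until 28 days after the last dose of study drug".
- **Analysis of adverse events.** "All adverse events reported during the adverse event reporting period will be considered as treatment-emergent adverse events" (Section 15.3.1). Incidence is also to be split by severity and by relationship to study drug, with all treated patients as the default denominator.
- **Analysis of laboratory data.** "A shift summary of baseline grade by maximum post-baseline CTCAE grade will be presented, as appropriate" (Section 15.3.2). Patients who reach Grade 3 or higher are also summarized. No end date is given for the post-baseline period.
- **Laboratory sampling in follow-up.** "Patients should be evaluated for safety up to 28 days after the last dose of study treatment" (Safety Follow-Up footnote, Appendix 2; the other schedules match). Hematology and chemistry at that visit are drawn only when clinically indicated.
- **New therapy.** "Any new anti-cancer therapies initiated within the safety follow-up visit (including drug name and date of initiation) will be recorded as well" (Section 10.4.3). Under Prohibited Therapies, within the same section: "No other hormonal therapy, chemotherapy, immunotherapy, or experimental anti-cancer medications will be permitted while the patient is in the study". Nothing says whether being in the study includes the 28 days after the last dose.
- **Causality.** Table 10 makes an event related by default, unless there is evidence of another cause or no plausible timing. Concomitant medication is one of the other causes it names.

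**The concern.** The protocol foresees that some patients will start another anti-cancer drug during safety follow-up, and it collects the date on which they do. No analysis in Section 15.3 uses that date. An event caused by the next drug is then tabulated as emerging on GDC-0810.

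Safety is a primary objective in Phases Ia and Ib and a secondary one in Phase IIa (Sections 6.1 and 6.2). The tables are single-arm, so no comparator shows how much of a rate belongs to something else. The identified risks of GDC-0810 are diarrhea, vomiting and nausea (Section 1.1). These are not specific to it: Section 2.2 lists nausea and diarrhea among the commonest non-hematologic reactions to palbociclib, for example. Stopping for progression, or because supply has run out, makes an early switch plausible, but the documents do not say how often it happens.

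**Working it through.** The plan gives no figure to reproduce. The check sets the rules side by side and then shows the scale.

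**1. Is there a cut-off anywhere?** Sections 12.2.1, 12.3.2.2 and 12.5 all end the period at 28 days after the last dose, and none ends it earlier. Section 15.3.1 adds no exclusion. Section 10.4.3 supplies a start date that Section 15.3 does not take up. The gap is real for adverse events.

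**2. Which tables are exposed?**
- *All-cause incidence:* fully exposed.
- *All-cause severity:* exposed. For a persistent event, Section 12.2.5.3 has the most extreme grade recorded, so a mild event on GDC-0810 that worsens on the next drug carries the higher grade.
- *Tables by relationship:* partly protected. The investigator can name the new drug as the cause, but the default runs the other way.
- *Laboratory shift and Grade 3 or higher:* exposed only through the open-ended maximum, and only for follow-up values that are drawn and entered.

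**3. How much of the window can overlap?** For a start on day d after the last dose, the overlap is (28 − d)/28:
- d = 7: 21/28 = 75%
- d = 14: 14/28 = 50%
- d = 21: 7/28 = 25%

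**4. What does one misplaced event do?** The change is 1/N.

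| Group | N (source) | Change |
|---|---|---|
| Phase IIa | about 100 (15.2.2) | 1.0 point |
| Cohort D1 | 6 (1.1) | 16.7 points |
| Cohort C1 | 4 (1.1) | 25.0 points |

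**5. Illustration on assumed rates.** Let f be the share of patients who start new therapy in the window, q the chance that it causes a given event there, and b the incidence already counted. If q does not depend on earlier events, the added incidence is f × q × (1 − b). The documents give neither f nor q. The ranges f = 10–50% and q = 10–40% are assumptions.

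| f | q | b = 0 | b = 44% |
|---|---|---|---|
| 10% | 10% | 1.0 | 0.6 |
| 25% | 20% | 5.0 | 2.8 |
| 50% | 40% | 20.0 | 11.2 |

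(Percentage points.) The 44% is the Phase IIa diarrhea rate in Section 1.1. It is a drug-related rate and only stands in for the all-cause rate, which is not given. A higher true base would shrink the increase. The table shows how the result depends on its inputs and does not estimate the effect.

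**The case against.** **New therapy may already be barred.** If a patient in safety follow-up is still in the study, the Prohibited Therapies paragraph excludes the overlap. That reading is possible, but the text does not settle it, and Section 10.4.3 provides for recording such starts. A prohibition also would not take an event out of the tables once a patient had switched.

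**Relatedness handles it.** In part. The dose-limiting toxicity rules use related events in a window of 28 or 35 days from the start of dosing (Section 10.2), so dose-finding is largely untouched. The frequency lists in Section 1.1 are also of related events. The same section, however, reports venous thromboembolism and acute renal failure regardless of relatedness, so all-cause counts are used. Section 15.3.1 also says that patients with repeated events are counted once, at the worst severity attributed to study drug. If that applies beyond the related tables, it limits the severity effect, but it does not remove a first occurrence from incidence.

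**A fixed 28-day window is conservative, and the programme is halted.** Both points stand. The analysis is descriptive and no decision is shown to turn on these tables, which lowers the stakes. Collection should not change.

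**Stronger readings that the documents do not support.**
- A reader might take the half-life ("The mean terminal half-life was approximately 8 hours", Section 1.2) to show that nearly the whole tail is off drug: 28 × 24/8 = 84 half-lives. That questions the 28-day tail itself. It does not measure contamination by a next drug, and the remedy here keeps the tail for every patient who does not switch.
- Likewise, 28 days against the Phase IIa median of 77 treatment days is 28/77 = 36%. That median is preliminary, and incidence is per patient treated rather than per unit of time.
- A reader might infer that laboratory grades are all counted as treatment-emergent. Section 15.3.1 applies that term to adverse events only.
- A reader might add next-drug nausea to the 38% in Section 1.1. That is a drug-related rate, so it is the wrong base for the all-cause table.

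**Conclusion.** The point holds for the all-cause adverse event incidence and severity tables: the rule as written admits events caused by the next anti-cancer drug, and the date that would separate them is collected but unused. It holds in part for the tables by relationship. It holds to a smaller degree for the laboratory summaries, and only where clinically indicated follow-up values reach the database.

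The total effect cannot be derived from the documents, because the rate of switching within 28 days, the event rate after switching and the all-cause base rates are all absent. What can be stated is the effect of one misplaced event: about 1 point at N=100, about 17 points in Cohort D1 and 25 points in Cohort C1. The documents do not support saying that the reported rates are materially wrong, or that dose selection is affected. This is a worthwhile and inexpensive improvement to the analysis rules.

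**What to change.** Leave adverse event collection and expedited reporting as they are.

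- **Sections 15.3.1 and 15.3.2:** base the main tables on events and laboratory values from the first dose to the earlier of (a) 28 days after the last dose and (b) the day before the first new systemic anti-cancer therapy. Tabulate the rest of the 28-day window separately, labelled as after the start of new anti-cancer therapy.
- **Persistent events:** use the dated grade changes that Section 12.2.5.3 already captures, so that worsening after the switch goes to the separate table.
- **Section 10.4.3:** reconcile the recording of new anti-cancer therapy in safety follow-up with the Prohibited Therapies paragraph, and state whether the latter covers the 28 days after the last dose.

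The cost is about two sentences in Section 15.3, one clarification in Section 10.4.3 and one derived flag from a date already collected. The downside is that a late GDC-0810 effect that first appears after the next therapy starts leaves the main table. It stays visible in the separate one. For events such as venous thromboembolism the two tables should be read together.
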